5.3.2 Eliciting Adverse Event Information

A consistent methodology of non-directive questioning should be adopted for eliciting adverse event information at all patient evaluation timepoints. Examples of non-directive questions include the following:

"How have you felt since your last clinic visit?"

"Have you had any new or changed health problems since you were last here?"

5.3.3 Assessment of Severity of Adverse Events

Table 3 provides guidance for assessing adverse event severity.

Table 3 Adverse Event Severity Grading Scale

Severity	Description
Mild	Discomfort noticed, but no disruption of normal daily activity
Moderate	Discomfort sufficient to reduce or affect normal daily activity
Severe	Incapacitating with inability to work or to perform normal daily activity

Note: Regardless of severity, some events may also meet seriousness criteria. Refer to definition of a serious adverse event (see Section 5.2.2).

5.3.4 Assessment of Causality of Adverse Events

Investigators should use their knowledge of the patient, the circumstances surrounding the event, and an evaluation of any potential alternative causes to determine whether an adverse event is considered to be related to the study drug, indicating "yes" or "no" accordingly. The following guidance should be taken into consideration.

- Temporal relationship of event onset to the initiation of study drug
- Course of the event, with special consideration of the effects of dose reduction, discontinuation of study drug, or reintroduction of study drug (as applicable)
- Known association of the event with the study drug or with similar treatments
- Known association of the event with the disease under study
- Presence of risk factors in the patient or use of concomitant medications known to increase the occurrence of the event

- Presence of non-treatment-related factors that are known to be associated with the occurrence of the event

5.3.5 Procedures for Recording Adverse Events

Investigators should use correct medical terminology/concepts when recording adverse events on the Adverse Event eCRF. Avoid colloquialisms and abbreviations.

Only one adverse event term should be recorded in the event field on the Adverse Event eCRF.

5.3.5.1 Infusion-Related Reactions

Adverse events that occur during or within 24 hours after study drug administration and are judged to be related to study drug infusion should be captured as a diagnosis (e.g., "infusion-related reaction") on the Adverse Event eCRF. If possible, avoid ambiguous terms such as "systemic reaction." Associated signs and symptoms should be recorded on the dedicated Infusion-Related Reaction eCRF. If a patient experiences both a local and systemic reaction to the same dose of study drug, each reaction should be recorded separately on the Adverse Event eCRF, with signs and symptoms also recorded separately on the dedicated Infusion-Related Reaction eCRF.

5.3.5.2 Diagnosis versus Signs and Symptoms

For adverse events other than infusion-related reactions (see Section [5.3.5.1](#)), a diagnosis (if known) should be recorded on the Adverse Event eCRF rather than individual signs and symptoms (e.g., record only liver failure or hepatitis rather than jaundice, asterixis, and elevated transaminases). However, if a constellation of signs and/or symptoms cannot be medically characterized as a single diagnosis or syndrome at the time of reporting, each individual event should be recorded on the Adverse Event eCRF. If a diagnosis is subsequently established, all previously reported adverse events based on signs and symptoms should be nullified and replaced by one adverse event report based on the single diagnosis, with a starting date that corresponds to the starting date of the first symptom of the eventual diagnosis.

5.3.5.3 Adverse Events That Are Secondary to Other Events

In general, adverse events that are secondary to other events (e.g., cascade events or clinical sequelae) should be identified by their primary cause, with the exception of severe or serious secondary events. A medically significant secondary adverse event that is separated in time from the initiating event should be recorded as an independent event on the Adverse Event eCRF. For example:

- If vomiting results in mild dehydration with no additional treatment in a healthy adult, only vomiting should be reported on the eCRF.
- If vomiting results in severe dehydration, both events should be reported separately on the eCRF.
- If a severe gastrointestinal hemorrhage leads to renal failure, both events should be reported separately on the eCRF.

- If dizziness leads to a fall and consequent fracture, all three events should be reported separately on the eCRF.
- If neutropenia is accompanied by an infection, both events should be reported separately on the eCRF.

All adverse events should be recorded separately on the Adverse Event eCRF if it is unclear as to whether the events are associated.

5.3.5.4 Persistent or Recurrent Adverse Events

A persistent adverse event is one that extends continuously, without resolution, between patient evaluation timepoints. Such events should only be recorded once on the Adverse Event eCRF. The initial severity (intensity or grade) of the event will be recorded at the time the event is first reported. If a persistent adverse event becomes more severe, the most extreme severity should also be recorded on the Adverse Event eCRF. Details regarding any increases or decreases in severity will be captured on the Adverse Event Intensity or Grade Changes eCRF. If the event becomes serious, it should be reported to the Sponsor immediately (i.e., no more than 24 hours after learning that the event became serious; see Section 5.4.2 for reporting instructions). The Adverse Event eCRF should be updated by changing the event from "non-serious" to "serious," providing the date that the event became serious, and completing all data fields related to serious adverse events.

A recurrent adverse event is one that resolves between patient evaluation timepoints and subsequently recurs. Each recurrence of an adverse event should be recorded as a separate event on the Adverse Event eCRF.

5.3.5.5 Abnormal Laboratory Values

Not every laboratory abnormality qualifies as an adverse event. A laboratory test result must be reported as an adverse event if it meets any of the following criteria:

- Is accompanied by clinical symptoms
- Results in a change in study treatment (e.g., dosage modification, treatment interruption, or treatment discontinuation)
- Results in a medical intervention (e.g., potassium supplementation for hypokalemia) or a change in concomitant therapy
- Is clinically significant in the investigator's judgment

It is the investigator's responsibility to review all laboratory findings. Medical and scientific judgment should be exercised in deciding whether an isolated laboratory abnormality should be classified as an adverse event.

If a clinically significant laboratory abnormality is a sign of a disease or syndrome (e.g., ALP and bilirubin 5× ULN associated with cholestasis), only the diagnosis (i.e., cholestasis) should be recorded on the Adverse Event eCRF.

If a clinically significant laboratory abnormality is not a sign of a disease or syndrome, the abnormality itself should be recorded on the Adverse Event eCRF, along with a descriptor indicating whether the test result is above or below the normal range (e.g., "elevated potassium," as opposed to "abnormal potassium"). If the laboratory abnormality can be characterized by a precise clinical term per standard definitions, the clinical term should be recorded as the adverse event. For example, an elevated serum potassium level of 7.0 mEq/L should be recorded as "hyperkalemia."

Observations of the same clinically significant laboratory abnormality from visit to visit should only be recorded once on the Adverse Event eCRF (see Section 5.3.5.4 for details on recording persistent adverse events).

5.3.5.6 Abnormal Vital Sign Values

Not every vital sign abnormality qualifies as an adverse event. A vital sign result must be reported as an adverse event if it meets any of the following criteria:

- Is accompanied by clinical symptoms
- Results in a change in study treatment (e.g., dosage modification, treatment interruption, or treatment discontinuation)
- Results in a medical intervention or a change in concomitant therapy
- Is clinically significant in the investigator's judgment

It is the investigator's responsibility to review all vital sign findings. Medical and scientific judgment should be exercised in deciding whether an isolated vital sign abnormality should be classified as an adverse event.

If a clinically significant vital sign abnormality is a sign of a disease or syndrome (e.g., high blood pressure), only the diagnosis (i.e., hypertension) should be recorded on the Adverse Event eCRF.

Observations of the same clinically significant vital sign abnormality from visit to visit should only be recorded once on the Adverse Event eCRF (see Section 5.3.5.4 for details on recording persistent adverse events).

5.3.5.7 Abnormal Liver Function Tests

The finding of an elevated ALT or AST ($>3\times$ ULN) in combination with either an elevated total bilirubin ($>2\times$ ULN) or clinical jaundice in the absence of cholestasis or other causes of hyperbilirubinemia is considered to be an indicator of severe liver injury (as defined by Hy's Law). Therefore, investigators must report as an adverse event the occurrence of either of the following:

- Treatment-emergent ALT or AST $>3\times$ ULN in combination with total bilirubin $>2\times$ ULN
- Treatment-emergent ALT or AST $>3\times$ ULN in combination with clinical jaundice

The most appropriate diagnosis or (if a diagnosis cannot be established) the abnormal laboratory values should be recorded on the Adverse Event eCRF (see Section 5.3.5.2) and reported to the Sponsor immediately (i.e., no more than 24 hours after learning of the event), either as a serious adverse event or an adverse event of special interest (see Section 5.4.2).

5.3.5.8 Deaths

All deaths that occur during the protocol-specified adverse event reporting period (see Section 5.3.1), regardless of relationship to study drug, must be recorded on the Adverse Event eCRF and immediately reported to the Sponsor (see Section 5.4.2). This includes death attributed to progression of AD.

Death should be considered an outcome and not a distinct event. The event or condition that caused or contributed to the fatal outcome should be recorded as the single medical concept on the Adverse Event eCRF. Generally, only one such event should be reported. If the cause of death is unknown and cannot be ascertained at the time of reporting, "**unexplained death**" should be recorded on the Adverse Event eCRF. If the cause of death later becomes available (e.g., after autopsy), "unexplained death" should be replaced by the established cause of death. The term "**sudden death**" should not be used unless combined with the presumed cause of death (e.g., "sudden cardiac death").

If the death is attributed to progression of AD, "Alzheimer's disease progression" should be recorded on the Adverse Event eCRF.

Deaths that occur after the adverse event reporting period should be reported as described in Section 5.6.

5.3.5.9 Preexisting Medical Conditions

A preexisting medical condition is one that is present at the screening visit for this study. Such conditions should be recorded on the General Medical History and Baseline Conditions eCRF.

A preexisting medical condition should be recorded as an adverse event only if the frequency, severity, or character of the condition worsens during the study. When recording such events on the Adverse Event eCRF, it is important to convey the concept that the preexisting condition has changed by including applicable descriptors (e.g., "more frequent headaches").

5.3.5.10 Lack of Efficacy or Worsening of Alzheimer’s Disease

Events that are clearly consistent with the expected pattern of progression of the underlying disease should not be recorded as adverse events. These data will be captured as efficacy assessment data only. In most cases, the expected pattern of progression will be based on guidelines (e.g., National Institute on Aging and Alzheimer’s Association [NIAAA] New Diagnostic Criteria and Guidelines for AD). In rare cases, the determination of clinical progression will be based on symptomatic deterioration. However, every effort should be made to document progression through use of objective criteria. If there is any uncertainty as to whether an event is due to disease progression, it should be reported as an adverse event.

5.3.5.11 Hospitalization or Prolonged Hospitalization

Any adverse event that results in hospitalization (i.e., inpatient admission to a hospital) or prolonged hospitalization should be documented and reported as a serious adverse event (per the definition of serious adverse event in Section 5.2.2), except as outlined below.

An event that leads to hospitalization under the following circumstances should not be reported as an adverse event or a serious adverse event:

- Hospitalization for respite care
- Planned hospitalization required by the protocol (e.g., for study drug administration or insertion of access device for study drug administration)
- Hospitalization for a preexisting condition, provided that all of the following criteria are met:

The hospitalization was planned prior to the study or was scheduled during the study when elective surgery became necessary because of the expected normal progression of the disease

The patient has not experienced an adverse event.

An event that leads to hospitalization under the following circumstances is not considered to be a serious adverse event, but should be reported as an adverse event instead:

- Hospitalization that was necessary because of patient requirement for outpatient care outside of normal outpatient clinic operating hours

5.3.5.12 Adverse Events Associated with an Overdose or Error in Drug Administration

An overdose is the accidental or intentional use of a drug in an amount higher than the dose being studied. An overdose or incorrect administration of study treatment is not itself an adverse event, but it may result in an adverse event. All adverse events associated with an overdose or incorrect administration of study drug should be recorded on the Adverse Event eCRF. If the associated adverse event fulfills

seriousness criteria, the event should be reported to the Sponsor immediately (i.e., no more than 24 hours after learning of the event; see Section 5.4.2).

5.3.5.13 Patient-Centered or Observer-Reported Outcome Data

Adverse event reports will not be derived from patient-centered outcome (or observed-reported outcome) data by the Sponsor, and safety analyses will not be performed using patient-centered outcome (or observed-reported outcome) data. Although sites are not expected to review the patient-centered outcome (or observed-reported outcome) data, it is possible that an investigator could become aware of patient-centered outcome (or observed-reported outcome) data that may be indicative of an adverse event. Under these circumstances, the investigator will determine whether the criteria for an adverse event have been met and, if so, will report the event on the Adverse Event eCRF.

5.4 IMMEDIATE REPORTING REQUIREMENTS FROM INVESTIGATOR TO SPONSOR

Certain events require immediate reporting to allow the Sponsor to take appropriate measures to address potential new risks in a clinical trial. The investigator must report such events to the Sponsor immediately; under no circumstances should reporting take place more than 24 hours after the investigator learns of the event. The following is a list of events that the investigator must report to the Sponsor within 24 hours after learning of the event, regardless of relationship to study drug:

- Serious adverse events (defined in Section 5.2.2; see Section 5.4.2 for details on reporting requirements)
- Adverse events of special interest (defined in Section 5.2.2; see Section 5.4.2 for details on reporting requirements)
- Pregnancies (see Section 5.4.3 for details on reporting requirements)

The investigator must report new significant follow-up information for these events to the Sponsor immediately (i.e., no more than 24 hours after becoming aware of the information). New significant information includes the following:

- New signs or symptoms or a change in the diagnosis
- Significant new diagnostic test results
- Change in causality based on new information
- Change in the event's outcome, including recovery
- Additional narrative information on the clinical course of the event

Investigators must also comply with local requirements for reporting serious adverse events to the local health authority and IRB/EC.

5.4.2 Reporting Requirements for Serious Adverse Events and Adverse Events of Special Interest

5.4.2.1 Events That Occur prior to Study Drug Initiation

After informed consent has been obtained but prior to initiation of study drug, only serious adverse events caused by a protocol-mandated intervention should be reported. Investigators should *report* to the Sponsor or its designee immediately (i.e., no more than 24 hours after learning of the event).

5.4.2.2 Events That Occur after Study Drug Initiation

After initiation of study drug, serious adverse events and adverse events of special interest will be reported until 8 weeks after the last dose of study drug. Investigators should record all case details that can be gathered immediately (i.e., within 24 hours after learning of the event) on the Adverse Event eCRF and submit the report via the electronic data capture (EDC) system. A report will be generated and sent to Roche Safety Risk Management by the EDC system.

In the event that the EDC system is unavailable, the paper Clinical Trial Serious Adverse Event/Adverse Event of Special Interest Reporting Form provided to investigators should be completed and submitted to the Sponsor or its designee immediately (i.e., no more than 24 hours after learning of the event), either by faxing or by scanning and emailing the form using the fax number or email address provided to investigators. Once the EDC system is available, all information will need to be entered and submitted via the EDC system.

Instructions for reporting serious adverse events that occur >8 weeks after the last dose of study treatment are provided in Section 5.6.

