5. ASSESSMENT OF SAFETY

5.1 SAFETY PLAN

Crenezumab is not approved, and clinical development is ongoing. The safety plan for patients in this study is based on clinical experience with crenezumab in completed and ongoing studies. The anticipated important safety risks for crenezumab are outlined below. Refer to the Crenezumab Investigator's Brochure for a complete summary of safety information.

Several measures will be taken to ensure the safety of patients participating in this study. Eligibility criteria have been designed to exclude patients at higher risk for toxicities. Patients will undergo safety monitoring during the study, including assessment of the nature, frequency, and severity of adverse events. In addition, guidelines for managing adverse events, including criteria for dosage modification and treatment interruption or discontinuation, are provided below.

Investigators will assess the occurrence of adverse events and serious adverse events at all patient evaluation timepoints during the study. All adverse events and serious adverse events, whether volunteered by the patient, discovered by study personnel during questioning, or detected through physical examination, laboratory test, or other means, will be recorded in the patient's medical record and on the appropriate adverse event eCRF. Each recorded adverse event or serious adverse event will include a description of its duration (i.e., start and end dates), severity, seriousness according to regulatory criteria, if applicable, and suspected relationship to the investigational product, as well as any actions taken. Patients will be carefully followed for adverse events during the study, including a safety follow-up period of 16 weeks after the last dose of study drug.

An iDMC will review unblinded safety and efficacy data at regular intervals (see Section 3.2.1 and the iDMC Charter for further details).

5.1.1 **ARIA-E and ARIA-H**

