5.2.3 Adverse Events of Special Interest (Immediately Reportable to the Sponsor)

Adverse events of special interest are required to be reported by the investigator to the Sponsor immediately (i.e., no more than 24 hours after learning of the event; see Section [5.4.2](#) for reporting instructions). Adverse events of special interest for this study include the following:

- Cases of potential drug-induced liver injury that include an elevated ALT or AST in combination with either an elevated bilirubin or clinical jaundice, as defined by Hy's Law (see Section [5.3.5.7](#))
- Suspected transmission of an infectious agent by the study drug, as defined below:

Any organism, virus, or infectious particle (e.g., prion protein transmitting transmissible spongiform encephalopathy), pathogenic or non-pathogenic, is considered an infectious agent. A transmission of an infectious agent may be suspected from clinical symptoms or laboratory findings that indicate an infection in a patient exposed to a medicinal product. This term applies only when a contamination of the study drug is suspected.

- Pneumonia: In the Phase II program, a numerical imbalance in pneumonia cases was observed, with more events reported in crenezumab-treated patients versus placebo-treated patients. It is of paramount importance to carefully document any pneumonia cases and other serious respiratory infections that occur in this study, by means of providing all relevant information required by the eCRF. A chest X-ray is required under the following circumstances:

Serious and non-serious pneumonia

Serious and non-serious lower respiratory tract infections

Serious upper respiratory infections

In addition, whenever possible, additional relevant investigations should be conducted (e.g., WBC counts, pathogen identification by means of hemocultures, bronchoalveolar lavage).

When a pneumonia case is diagnosed, a blood sample for fluorescence-activated cell-sorting analysis must be collected as soon as feasible for the site and the patient.

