5.3.1 Adverse Event Reporting Period

Investigators will seek information on adverse events at each patient contact. All adverse events, whether reported by the patient or noted by study personnel, will be recorded in the patient's medical record and on the Adverse Event eCRF.

After informed consent has been obtained but prior to initiation of study drug, only serious adverse events caused by a protocol-mandated intervention (e.g., invasive procedures such as biopsies, discontinuation of medications) should be reported (see Section 5.4.2 for instructions for reporting serious adverse events).

After initiation of study drug, all adverse events will be reported until 4 elimination half-lives after the last dose of study drug and collected on the occasion of the safety follow-up visit (16 weeks after the last dose of study drug).

Instructions for reporting adverse events that occur after the adverse event reporting period are provided in Section 5.6.

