5.6 ADVERSE EVENTS THAT OCCUR AFTER THE ADVERSE EVENT REPORTING PERIOD

The Sponsor should be notified if the investigator becomes aware of any **serious** adverse event that occurs after the end of the adverse event reporting period (defined as 16 weeks after the last dose of study drug), if the event is believed to be **related** to prior study drug treatment. These events should be reported through use of the Adverse Event eCRF. However, if the EDC system is not available, the investigator should report these events directly to the Sponsor or its designee, either by faxing or by scanning and emailing the paper Clinical Trial Serious Adverse Event/Adverse Event of Special Interest Reporting Form using the fax number or email address provided to investigators.

5.7 EXPEDITED REPORTING TO HEALTH AUTHORITIES, INVESTIGATORS, INSTITUTIONAL REVIEW BOARDS, AND ETHICS COMMITTEES

The Sponsor will promptly evaluate all serious adverse events and adverse events of special interest against cumulative product experience to identify and expeditiously

communicate possible new safety findings to investigators, IRBs, ECs, and applicable health authorities based on applicable legislation.

To determine reporting requirements for single adverse event cases, the Sponsor will assess the expectedness of these events using the following reference document:

- Crenezumab Investigator's Brochure
- *PET Ligand Investigator's Brochures*

The Sponsor will compare the severity of each event and the cumulative event frequency reported for the study with the severity and frequency reported in the applicable reference document.

Reporting requirements will also be based on the investigator's assessment of causality and seriousness, with allowance for upgrading by the Sponsor as needed.

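### Section 5.4.2.2 stops SAE and AESI reporting at 8 weeks after the last dose and refers later SAEs to Section 5.6, which starts only after 16 weeks

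*Combined protocol and SAP*

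**What the plan says.** Section 5.4.2.2, which tells sites how to report after study drug has started, says that "serious adverse events and adverse events of special interest will be reported until 8 weeks after the last dose of study drug". It then adds: "Instructions for reporting serious adverse events that occur >8 weeks after the last dose of study treatment are provided in Section 5.6". That pointer names SAEs only.

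Section 5.6 takes over only once the "adverse event reporting period (defined as 16 weeks after the last dose of study drug") has ended. It covers only serious events that are believed related to prior study drug.

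Other sections that bear on the window:

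- Section 5.1 has patients followed for adverse events, "including a safety follow-up period of 16 weeks after the last dose of study drug".
- Section 5.3.1 says "all adverse events will be reported until 4 elimination half-lives after the last dose of study drug", with collection at the 16-week safety visit.
- Section 5.3.5.8 covers "All deaths that occur during the protocol-specified adverse event reporting period (see Section 5.3.1), regardless of relationship to study drug". It requires immediate reporting and refers to Section 5.4.2 for the method.
- Section 5.2.3 says "Adverse events of special interest are required to be reported by the investigator to the Sponsor immediately", and lists pneumonia among these events.
- Section 5.4 requires 24-hour reporting of SAEs and AESIs whatever the causality: "under no circumstances should reporting take place more than 24 hours after the investigator learns of the event". It gives no end date.
- Appendix 1, footnote u, limits adverse event collection at the final annual visit to study-related SAEs and cites Section 5.6.

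**The concern.** The section that holds the operative reporting instructions ends at 8 weeks and passes later SAEs to a section whose own scope has not begun. A site that reads Section 5.4.2.2 literally has no valid instruction for an SAE at, say, week 12. If it applies Section 5.6 early, it will report only related SAEs, against the all-causality rule in Section 5.4. Ordinary adverse events would also be reportable for longer than serious ones.

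Long-term safety is the primary objective, and pneumonia is the AESI that the objectives table singles out. Section 1.3.7 rests part of the benefit-risk case on 24-hour reporting of pneumonia, other serious respiratory infections and deaths. Section 5.7 has the sponsor evaluate SAEs and AESIs promptly, which depends on receiving them promptly. With about 350 centers, different readings at different sites are likely.

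**Working it through.** The plan gives no computed figure to reproduce. The check sets the stated windows side by side and then does some simple arithmetic.

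**1. Windows, counted from the last dose**

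| Section | Events | End or start |
|---|---|---|
| 5.4.2.2 | SAEs and AESIs | ends at 8 weeks |
| 5.4.2.2, pointer to 5.6 | SAEs only | after 8 weeks |
| 5.6 | related SAEs only | starts after 16 weeks |
| 5.3.1 | all adverse events | ends at 4 half-lives; collected at 16 weeks |
| 5.3.5.8 | all deaths, immediately, via 5.4.2 | the 5.3.1 period |
| 5.1 | safety follow-up | 16 weeks |

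The stretch covered by neither 5.4.2.2 nor 5.6 is 16 − 8 = 8 weeks, half of the follow-up.

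**2. The half-life window**

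Section 1.2.5 gives a terminal half-life of 17–26 days after a single IV dose, and 18–23 days with weekly dosing. Weeks = 4 × half-life in days / 7.

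- Single dose: 4 × 17 = 68 days = 9.7 weeks; 4 × 26 = 104 days = 14.9 weeks.
- Weekly dosing: 4 × 18 = 72 days = 10.3 weeks; 4 × 23 = 92 days = 13.1 weeks.
- On the single-dose range, the 5.3.1 period outlasts 8 weeks by 1.7 to 6.9 weeks and ends 1.1 to 6.3 weeks before Section 5.6 begins.
- For 8 weeks to equal 4 half-lives, the half-life would have to be 56 / 4 = 14 days, below every value given. For 16 weeks it would have to be 112 / 4 = 28 days, above every value given.

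**3. Tracing two events**

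- Unrelated SAE at week 9: outside 5.4.2.2, referred to 5.6, and outside 5.6 on both timing and causality. It is inside the 5.3.1 period at every half-life above. If it is fatal, 5.3.5.8 requires immediate reporting through 5.4.2, which has already stopped.
- Non-serious pneumonia at week 9: outside 5.4.2.2 and not named in the pointer to 5.6. Sections 5.2.3 and 5.4 still set a 24-hour duty, but both send the reader to 5.4.2 for instructions.

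**4. Footnote u**

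Doses before Week 53 fall at Weeks 1, 5, …, 49, which is (49 − 1)/4 + 1 = 13 doses. The gap from last dose to Week 53 is 53 − 37 = 16, 53 − 41 = 12, 53 − 45 = 8 and 53 − 49 = 4 weeks. So 4 of the 13 possible last-dose weeks put the final annual visit no later than 16 weeks after the last dose. For Week 105 the same holds for last doses at Weeks 89, 93, 97 and 101. At those visits the footnote applies the post-period rule while the 16-week period is still open.

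**The case against.** The best defence is that 8 weeks is a deliberately shorter expedited window inside a 16-week collection window. Section 5.1 can be read that way, and general 24-hour rules without an end date do not by themselves contradict the section they refer to for detail. But Section 5.6 would then have to take over at 8 weeks, and it does not. Section 5.3.5.8 would also have to stop immediate reporting of deaths at 8 weeks, and it does not. The 8-week pregnancy window in Section 5.4.3 is a separate rule and reconciles nothing.

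Several narrower points stand:

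- Section 5.3.1 may simply mean 16 weeks, loosely expressed in half-lives. The main conflict is then 8 against 16 weeks.
- The half-lives come from a Phase I study at 0.3–10 mg/kg single dose and 0.5–5 mg/kg weekly, not from 60 mg/kg every 4 weeks. Section 1.2.5 reports dose-proportional kinetics, so they are a reasonable proxy, but part of that section is redacted.
- In all four footnote u cases the 4-week safety visit falls at Weeks 41 to 53, at most 12 weeks before Week 53. Section 4.6.1 allows the two visits to be combined, and the 4-week column collects all adverse events, as does the 16-week visit. The 4 of 13 therefore counts overlapping rules, not lost reports.
- Only patients who stop crenezumab have this follow-up. The scheduled safety visits are at 4 and 16 weeks, so a site may learn of many week 8–16 events only at week 16 under either rule. A case entered and submitted in the EDC system also generates a safety report automatically.

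These points limit the practical effect. None supplies the missing instruction for weeks 8 to 16.

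**Conclusion.** The contradiction is real, and nothing in the protocol resolves it. The firm conflicts are Section 5.4.2.2 against Section 5.6, with an 8-week gap, and Section 5.4.2.2 against Section 5.3.5.8 on deaths. Neither depends on the exact half-life, as long as it exceeds 14 days. The ranges in weeks for Section 5.3.1 assume that the Phase I half-lives carry over to the study dose. Footnote u is a related but secondary inconsistency.

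The consequence is delayed or omitted expedited reports of SAEs and AESIs in the second half of follow-up. Collection at the 16-week visit continues, no analysis estimate is affected, and the number of events involved cannot be derived from the documents. This should be fixed.

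**What to change.** State one reporting period for SAEs and AESIs and use it in Sections 5.3.1, 5.4.2.2 and 5.6. The least disruptive way is to put the 16-week period already in Sections 5.1 and 5.6 in both places where 5.4.2.2 now says 8 weeks, and to give the same end in 5.3.1 instead of a number of half-lives. The period for deaths in 5.3.5.8 then follows through its reference to 5.3.1. Reword footnote u so that its restriction to study-related SAEs applies only when the final annual visit falls after that period, and say which rule governs a combined visit.

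The cost is a few words in an amendment and a memo to sites. The 16-week visit already collects adverse events, so no visit is added. The downside is a small number of additional expedited reports.
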